Statistical Analysis Plan

Document Control

Title: Statistical Analysis Plan for the Study of SGLT2 Inhibitors in Lupus Nephritis Patients

Protocol ID: [NCT05748925] Version: 1.0 Date: [11/3/2024] Principal Investigator: [[name]] Statistician: [[name]] Approval Signatures: Principal Investigator: [name] Statistician: [name]

Table of Contents

- 1. Introduction
- 2. Study Design
- 3. Study Objectives
- 4. Endpoints
- 5. Sample Size Justification
- 6. Statistical Methods
- 7. Handling of Missing Data
- 8. Interim Analysis
- 9. Safety Analysis
- 10. Data Quality and Management
- 11. Software
- 12. Appendices

1. Introduction

• **Purpose of the SAP**: This document outlines the statistical approach for analyzing data from the clinical trial studying the effects of SGLT2 inhibitors on renal, cardiovascular, and hematological outcomes in lupus nephritis patients.

2. Study Design

Design: Randomized, double-blind, placebo-controlled clinical trial.

Study Duration: Conducted from September 2022 to November 2023

Randomization: Patients were randomly assigned to either dapagliflozin (10 mg once daily) or placebo groups using computer-generated random tables in a 1:1 ratio stratified by age and gender.

Blinding: The study was double-blinded, and all trial staff and participants remained unaware of individual treatment assignments until study completion.

3. Study Objectives

Primary Objective: To evaluate the impact of SGLT2 inhibitors on renal, cardiovascular, and hematological parameters in lupus nephritis patients.

Secondary Objective: To explore changes in body weight, BMI, and other echocardiographic and iron profile parameters over 12 months.

4. Endpoints

Primary Endpoints

Renal Function: Serum creatinine, eGFR, and 24-hour urine protein

Cardiovascular Health: BNP levels and coronary calcification via NCCT

Hematological Parameters: Hemoglobin and erythropoietin levels

Hepcidin Level: Measured before and after intervention

Secondary Endpoints

Body Weight and BMI: Assessed at baseline and follow-up visits.

Echocardiographic Findings: Assessed pre- and post-intervention.

Iron Profile: Serum ferritin and TSAT

5. Sample Size Justification

Calculation: A sample size of 100 patients was targeted, accounting for potential dropouts, to provide sufficient power (80%) at a significance level of 0.05 to detect differences between the two groups.

6. Statistical Methods

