
General Considerations

Significance Level: A two-sided alpha level of 0.05 will be used for all primary analyses.

Analysis Populations:

Intent-to-Treat (ITT): All randomized patients will be analyzed according to their assigned group.

Per-Protocol (PP): Only patients completing the study without major protocol violations.

Primary Endpoint Analysis

Renal Outcomes: ANOVA for repeated measures for serum creatinine and eGFR if normally distributed, and the Friedman test for non-normally distributed data. Post-hoc tests using Bonferroni correction.

Cardiovascular Outcomes: Mann-Whitney U test for BNP levels and coronary calcification between groups.

Hematological Outcomes: Paired t-test for hemoglobin and erythropoietin levels if data is normally distributed; otherwise, Wilcoxon signed-rank test.

Secondary Endpoint Analysis

Body Weight and BMI: Compared over time using ANOVA for repeated measures.

Echocardiographic Parameters: Analyzed with paired t-tests, adjusted with Bonferroni correction.

Iron Profile: Analyzed pre- and post-intervention using ANOVA or Kruskal-Wallis for non-normally distributed variables.

Categorical Variables

Chi-Square Test: For between-group comparisons of categorical data (e.g., presence of diabetes, hypertension).

7. Handling of Missing Data

Imputation: Last observation carried forward (LOCF) for data missing at random; multiple imputation for extensive missing data.

Sensitivity Analysis: Conducted to evaluate the robustness of primary endpoint findings against different missing data assumptions.

8. Interim Analysis

Timing: An interim analysis is planned at the halfway point (6 months).

Stopping Rules: An O'Brien-Fleming approach will be applied to adjust the significance threshold for interim testing, allowing for an earlier stop for efficacy or safety concerns.

9. Safety Analysis

Adverse Events (AEs): Summarized by type, frequency, and severity. Fisher's exact test will be used to compare AE rates between groups.

Specific Safety Parameters: Monitoring for hypotension, electrolyte imbalances, and kidney function.

10. Data Quality and Management

Data Quality Measures: Includes data verification, regular audits, and query resolution.

Database Lock: Data will be locked and verified prior to the final analysis.

11. Software

Statistical Software: All analyses will be conducted using SPSS (Version 25).

12. Appendices

	Control group. (n= 41)	Study group. (n= 38)	P value

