Cholesterol mg/dL mean ± SD	185 ± 46	172 ± 40.7	0.5
Albumin (g/dL) mean ± SD	3.7 ± 0.4	3.7 ± 0.3	0.4
Random blood sugar (mg/dL) Median (min, max)	89 (66, 568)	92.5 (64, 243)	0.4
Uric acid (mg/dL) mean ± SD	6.2 ± 2.1	6.5 ± 1.7	0.2
Alanine aminotransferase (IU/L) Median (min, max)	17 (2, 84)	17 (7, 82)	0.8
Aspartate aminotransferase (IU/L) Median (min, max)	21(9, 66)	19 (12,72)	0.4
Sodium (mEq/L) mean ± SD	137 ± 3.1	136 ± 3	0.5
Potassium (mEq/L) mean ± SD	3.9 ± 0.4	4 ± 0.4	0.3

eGFR: estimated glomerular filtration rate; (Student T test or Mann-Whitney) for continuous data, and chisquare test for categorical data. Continuous data are expressed as mean (SD) or median (minimum – maximum). Categorical data are expressed as number (percentage). Level of significance < 0.05.

Table (4): Baseline hematological findings:

	Control group. (n= 41)	Study group. (n= 38)	P value		
Hemoglobin (g/dL) Mean \pm SD	11.9 ± 1.9	11.7 ± 1.7	0.5		
MCV (FL) Mean ± SD	82 ± 7	84 ± 6.9	0.9		
MCH (Pg) Mean ± SD	25.4 ± 2.9	26.3 ± 2.9	0.9		
Ferritin (mg/dL) Median (min, max)	60 (13, 1113)	33.5 (3, 1460)	0.09		
TSAT (%) Median (min, max)	23.8 (7, 64)	18 (6, 74)	0.05		
Erythropoietin level (IU/L) Mean ± SD	11.6 ± 2.1	11.3 ± 1.4	0.1		
Hepcidinlevel(ug/L) $Mean \pm SD$	198 ± 74	182 ± 76	0.3		
Platelet count (*10 ³) Mean \pm SD	288 ± 71	300 ± 79	0.7		

McW Mean corpuscle volume; MCH: Mean corpuscular hemoglobin; TSAT: Transferrin saturation test; (Student T test or Mann-Whitney) for continuous data, and chi-square test for categorical data. Continuous data are expressed as mean (SD) or median (minimum – maximum). Categorical data are expressed as number (percentage).; Level of significance < 0.05.

Table (5): Baseline Cardiac evaluation:

Control group. Study group. P value

	(n= 41)	(n= 38)	
Coronary calcification No. (%)	3 (7.3%)	11 (28.9%)	0.012
Coronary calcification severity No. (%) - No - Minimal - Mild - moderate	38 (92.7%) 1 (2.4%) 1 (2.4%) 1 (2.4%)	27 (71.1%) 3 (7.9%) 7 (18.4%) 1 (2.6%)	0.04
BNP (ng/L) Median (min, max)	52 (40, 557)	52 (34, 90)	0.8
Echocardiographic	c finding		0.6
EF % Mean \pm SD	65.4 ± 9.3	64.6 ± 5.4	0.6
LAD (ml) Mean ± SD	24.2 ± 7.6	24.9 ± 7.6	0.6
Aortic diameter (ml) Mean ± SD	24.7±7.4	24.8±7.1	0.9
ESV (ml/m) Median (min, max)	38±13.6	41±13.9	0.4
EDV (ml/m) Mean ± SD	98±35.7	111.5±31.6	0.08

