	P value**	0.5	0.7	0.7	0.3	0.6	
MCV (FL) Mean ± SD	Control	82±7	83±7	84±7	84.6±7.9	81.5±13	0.1
	Study	84±6.9	80±14	83±10	83.2±10.8	84±7	0.3
	P value**	0.9	0.1	0.5	0.5	0.4	
MCH (Pg) Mean ± SD	Control	25.4±2.9	27.3±9.8	28.5±9	26.9±3.2	26.9±3.1	0.08
	Study	26.3±2.9	27.3±9.5	27±3	26.6±3.5	27.1±3.4	0.8
	P value**	0.9	0.9	0.4	0.4	0.5	

(*) Within group analysis (repeated measure ANOVA).

(**) Between group analysis (Student T test or Mann-Whitney) for continuous data, and chi-square test for categorical data. Continuous data are expressed as mean (SD) or median (minimum – maximum). Categorical data are expressed as number (percentage).

MCV: Mean corpuscle volume; MCH: Mean corpuscular haemoglobin.

Table (8): other hematological findings differences between both groups:

	Grouping	Baseline	12 months	P value*
Ferritin (mg/dL)	Control	60 (13, 1113)	75 (6, 2127)	0.5
Median (min, max)	Study	33.5 (3, 1460)	64 (3, 1311)	0.8
	P value**	0.09	0.4	
TSAT (%) Median	Control	23.8 (7, 64)	28 (5, 62)	0.1
	Study	18 (6, 74)	20 (6, 66)	0.9
	P value**	0.05	0.1	
Erythropoietin	Control	11.6±2.1	12.8 ± 3.5	0.08
SD	Study	11.3±1.4	12.4 ± 3.5	0.1
	P value**	0.1	0.6	
Hepcidin level ug/L	Control	198 ± 74	128 ±63	0.001
Mean ± SD	Study	182±76	116±15	0.001
	P value**	0.3	0.2	
Platelet count	Control	288 ± 71	283 ± 74	0.6
(×10³) Mean ± SD	Study	300 ± 79	276 ± 65	0.01
	P value**	0.7	0.5	

(*) Within group analysis (paired t test).

(**) Between group analysis (Student T test or Mann-Whitney) for continuous data, and chi-square test for categorical data.

Continuous data are expressed as mean (SD) or median (minimum – maximum). Categorical data are expressed as number (percentage).

TSAT: Transferrin saturation test

Table (9): Cardiac evaluation differences between both groups after 12 months:

	Control group	Study group	P value
Coronary calcification No. (%)	1 (2.4%)	11 (28.9%)	0.001
Coronary calcification severity No. (%) - No - Minimal - Mild - moderate	40 (97.6%) 0 0 1 (2.4%)	27 (71.1%) 9 (23.7%) 2 (5.3%) 0	0.002
BNP ng/L Mean \pm Sd	66 ± 22.1	65.8±21	0.9
Echocardiographic findi	ng		
EF % Mean ± SD	65.5±5.8	64.9±5.2	0.8
LAD ml Mean \pm SD	26.7±7.6	28.2±8.6	0.4
Aortic diameter ml Mean ± SD	26.6±6.5	25.5±6.2	0.4
ESV ml/min Mean ± SD	39.5±18	36.3±9.3	0.3
EDV ml/min Mean ± SD	108±29.6	109±19.3	0.9

BNP: Brain natriuretic peptide; EF: Ejection fraction; LAD: Left atrial dimension; ESV: End- systolic volume; EDV:

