End diastolic volume; Chi square test; Student t- test; Man, Whitney test; Level of significance < 0.05.

Table (10): Comparison between both groups as regard post intervention side effects

	Control group. (n= 41)	Study group. (n=38)	P value
AKI episodes No. (%)			
- No	38 (92.7%)	31 (81.6%) 5 (13.2%)	0.17
- once	1 (2.4%) 2 (4.9%)	2 (5.3%)	
- twice			
UTI No. (%)			
- No	35 (85.4%) 4 (9.8%)	31 (81.6%) 5 (13.2%)	0.8
- once	2 (4.9%)	2 (5.3%)	
- more than once			
Gynecological infection No. (%)	1 (2.4%)	2 (5.3%)	0.6
Viral infection No. (%)	1(2.4%)	1 (2.6%)	1
MMF intolerance No. (%)	1 (2.5%)	2 (5.3%)	0.6
Renal biopsy No. (%)	2 (4.9%)	1 (2.6%)	0.6
Increase steroid dose No. (%)	7 (17.1%)	4 (10.5%)	1

UTI: urinary tract infection episodes; AKI: acute kidney injury; chi-square test for categorical data. Categorical data are expressed as number (percentage).; Level of significance < 0.05.

figure1: flow chart of participating populations

Figure (2) shows difference between individual which had improved eGFR or not as regard to their basal eGFR in total cohort, which found that improving eGFR had been occurred in patients with lower eGFR (107±50 vs 137±58 ml/min/m²

Figure (3) show no significant difference between the drug and placebo groups (p=0.857). as regard incidence of anemia before intervention, the drug group has 23 anemic participants (60.5%) versus 24 participants (58.5%) in the placebo group, while post intervention, In the anemia category, the drug group has 16 participants (42.1%), while the placebo group has 22 participants (53.7%) with non-significant differences (p = 0.3)

Figure (4) differences in body weight between both groups at different time points:

Glossary of Terms and Abbreviations

AA	Amino Acids
ABIN	A20 Binding Inhibitor Of NF-Kb
ACE	Angiotensin-Converting Enzyme Inhibitors
ACR	American College of Rheumatology
AKI	Acute Kidney Injury
ALCAM	Activated Leucocyte Adhesion Molecule
ALP	Alkaline Phosphatase
AMP	Adenosine Monophosphate
АМРК	Amp-Activated Protein Kinase
ANA	Antinuclear Antibodies
ANG II	Angiotensin 2
ANOVA	Analysis Of Variance
ANTI-DSDNA	Anti Double Stranded Deoxyribonucleic Acid
	Antibodies
ANTI-SM	Anti-Smith Antibodies
APLS	Antiphospholipid Syndrome
ARBS	Angiotensin 2 Receptor Blockers
ATN	Acute Tubular Necrosis
ATP	Adenosine Triphosphate
BAFF	B-Cell-Activating Factor
BLISS	B Lymphocyte Stimulator Inhibitor Belimumab
	Plus Standard Therapy
BMI	Body Mass Index
BNP	Brain Natriuretic Peptide
BP	Blood Pressure

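### The coronary calcification primary endpoint is undefined, and its planned test ignores a baseline imbalance that the 12-month result partly carries

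*SAP*

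**What the plan says.** SAP section 4 lists among the primary endpoints "Cardiovascular Health: BNP levels and coronary calcification via NCCT". It gives no scale, cut-off, timepoint or definition of change. SAP section 6 plans a "Mann-Whitney U test for BNP levels and coronary calcification between groups". The variable to be ranked is not named and baseline does not enter. Section 6 also has a general rule for categorical data, "Chi-Square Test: For between-group comparisons of categorical data (e.g., presence of diabetes, hypertension"), and sets the significance level: "A two-sided alpha level of 0.05 will be used for all primary analyses". The protocol's list of cardiovascular assessments speaks of the incidence of vascular calcification, which is a further reading.

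The SAP appendix gives the data. Table 5 (baseline) has "Coronary calcification No. (%) 3 (7.3%) 11 (28.9%) 0.012" and a four-level severity grade. Table 9 (12 months) has "Coronary calcification No. (%) 1 (2.4%) 11 (28.9%) 0.001" and the same four-level grade with p=0.002. The footnote to Table 9 lists chi-square, Student t and Mann-Whitney without tying any of them to a row.

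**The concern.** A primary endpoint should point to one variable, at one time, with one deciding comparison. Here several readings are open, and the results are already printed in the same document.

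The gap matters because of where the results fall. The 12-month between-arm p-values for the other SAP primaries are 0.8 (creatinine), 0.9 (eGFR), 0.6 (24-hour protein), 0.9 (BNP), 0.6 (haemoglobin), 0.6 (erythropoietin) and 0.2 (hepcidin). Calcification alone is below 0.05, and it points against the study drug. A between-group test of the 12-month scan treats the arms as if they had started level, and Table 5 shows that they did not. A reader could take p=0.001 as an effect of treatment when much of the gap was there before treatment.

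**Working it through.** **Inputs.** Arm sizes are 41 control and 38 study (column heads of Tables 5 and 10; the Table 9 percentages agree). Grades in the order none/minimal/mild/moderate, scored 0, 1, 2, 3:

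| | Control | Study |
|---|---|---|
| Baseline (Table 5) | 38/1/1/1 | 27/3/7/1 |
| 12 months (Table 9) | 40/0/0/1 | 27/9/2/0 |

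**Step 1: the printed p-values.**
- Presence at 12 months, 1/41 v 11/38: Pearson chi-square 10.76, p=0.0010 (Fisher 0.0012). Printed 0.001.
- Severity at 12 months: Pearson chi-square 14.43 on 3 df, p=0.0024. Tie-corrected Mann-Whitney on the grade, p=0.0016. Both round to the printed 0.002.
- Presence at baseline, 3/41 v 11/38: Pearson chi-square 6.33, p=0.012, as printed.
- Mann-Whitney on the baseline grade: p=0.014.

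The three 12-month results agree in direction and are all below 0.05.

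**Step 2: how much of the gap was there at baseline.** For presence, the gap is 28.9 − 7.3 = 21.6 points at baseline and 28.9 − 2.4 = 26.5 points at 12 months. The study arm has 11 cases at both times and control goes from 3 to 1. For mean grade:
- Baseline: control 6/41 = 0.146, study 20/38 = 0.526, difference 0.380.
- 12 months: control 3/41 = 0.073, study 13/38 = 0.342, difference 0.269.

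**Step 3: what adjustment could do.** With linear adjustment, adjusted difference = 12-month difference − b × baseline difference, where b is the pooled within-arm slope of 12-month on baseline grade. The slope depends on which patients moved, which is not printed, but its maximum can be found by sorting both scans in the same order within each arm.
- Within-arm sums of squares at baseline: (14 − 6²/41) + (40 − 20²/38) = 13.12 + 29.47 = 42.60.
- Largest within-arm cross-products: (9 − 6×3/41) + (25 − 20×13/38) = 8.56 + 18.16 = 26.72.
- Maximum b = 26.72/42.60 = 0.627.
- Smallest adjusted difference = 0.269 − 0.627 × 0.380 = +0.03.

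Precision under that pairing:
- Within-arm sum of squares at 12 months: (9 − 3²/41) + (17 − 13²/38) = 21.33.
- Residual: 21.33 − 0.627 × 26.72 = 4.57 on 76 df, so variance 0.0602.
- SE = √[0.0602 × (1/41 + 1/38 + 0.380²/42.60)] = 0.057.
- t = 0.0306/0.057 = 0.54, p about 0.59.

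If b were 0, the difference would stay at +0.27. Any b from 0 to 0.627 gives a value from +0.27 down to +0.03.

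**Step 4: the same bound for presence.**
- Maximum b = (0.927 + 7.816)/(2.780 + 7.816) = 0.825.
- Smallest adjusted difference = 0.2651 − 0.825 × 0.2163 = +0.087.
- Residual: (0.976 + 7.816) − 0.825 × 8.743 = 1.58 on 76 df; SE about 0.034; t about 2.56, p about 0.012.

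So under this pairing the grade signal largely disappears, while the presence signal shrinks but does not vanish.

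**The case against.** The strongest reply is that the measures actually reported agree, that section 6 already implies a ranked variable, and that Table 9 reports one. Presence is covered by the SAP's general rule for categorical data. The severity p-value may well be the planned Mann-Whitney, since that test and chi-square both round to 0.002. The imbalance is also a chance event, and an unadjusted comparison in a randomised trial is valid on average. All of this stands. It limits the point to the missing definition and the missing baseline term. Validity on average does not rescue the reading of this particular result, where the arms are known to have differed on the endpoint itself before treatment.

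A reader might infer more than the documents support:
- *The choice of measure reverses the result.* It does not among the reported 12-month measures. A cut at mild or worse gives 1/41 v 2/38, Fisher p=0.61, but that cut-off is in neither document, rests on 3 events and keeps the same direction (2.4% v 5.3%).
- *Presence and grade point opposite ways once baseline is considered.* Only raw changes do: +4.9 points for presence and −0.11 for mean grade (p=0.17 and 0.19 under sorted pairing). Under linear adjustment both differences stay positive for every pairing that the printed counts allow.
- *The severity row departs from the planned test.* This cannot be shown, because the footnote assigns no test to it.

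**Conclusion.** The point holds as a gap in definition together with an unadjusted planned test. The variable, timepoint and baseline handling are not stated, and the one SAP primary below 0.05 at 12 months partly carries a pre-treatment difference (3/41 v 11/38, p=0.012). Adjustment could change the conclusion on grade, from +0.27 unadjusted to as little as +0.03 (p about 0.59).

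This is a bound and not an estimate. It assumes equally spaced 0-3 scores, a linear model on sparse data and the pairing most favourable to adjustment. The p-values under that pairing are rough. The documents do not support a statement that adjustment removes the difference, nor a claim of harm, no effect or benefit. Only the paired patient records can settle the size.

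**What to change.** In SAP section 4, define one variable: the ordered NCCT severity grade (none, minimal, mild, moderate) at 12 months. In section 6, replace the unadjusted Mann-Whitney for calcification with one named arm comparison that includes the baseline grade, either a proportional-odds model or a rank-based equivalent, reported with a 95% CI. Label it as specified after the data were seen, because the SAP already contains the results. In Table 9, give that single estimate in place of the two p-values, and show presence and the baseline-by-12-month cross-table by arm as description only.

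The cost is SAP wording and one re-run on data already held. The downsides are a wide interval, because few patients have any calcification (14 of 79 at baseline, 12 of 79 at 12 months), and the loss of p=0.001 as a primary result.

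### SAP section 6 plans no baseline-adjusted drug-versus-placebo contrast: six of eight primary endpoints have no stated between-arm test, and coronary calcification is compared unadjusted despite a baseline gap

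*SAP*

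**What the plan says.** SAP section 4 lists eight primary endpoints: three renal ("Serum creatinine, eGFR, and 24-hour urine protein"), BNP, coronary calcification, haemoglobin, erythropoietin and hepcidin. Section 5 justifies the sample size by power for a difference between the groups. Section 2 says randomisation was stratified by age and gender.

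Section 6 then assigns these tests:

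- Renal: the first choice is "ANOVA for repeated measures for serum creatinine and eGFR if normally distributed". The fallback is worded "and the Friedman test for non-normally distributed data". No treatment factor or group-by-time term is stated, and 24-hour urine protein is not named.
- Cardiovascular: "Mann-Whitney U test for BNP levels and coronary calcification between groups".
- Haematological: "Hematological Outcomes: Paired t-test for hemoglobin and erythropoietin levels if data is normally distributed; otherwise, Wilcoxon signed-rank test".
- Hepcidin: no test.
- Secondary endpoints: the iron line reads "Iron Profile: Analyzed pre- and post-intervention using ANOVA or Kruskal-Wallis for non-normally distributed variables"; the line on weight reads "Body Weight and BMI: Compared over time using ANOVA for repeated measures"; the line on cardiac ultrasound reads "Echocardiographic Parameters: Analyzed with paired t-tests, adjusted with Bonferroni correction".

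No covariate, ANCOVA, mixed model or change-score comparison appears in section 6. The footnotes to Tables 6 and 7 (SAP section 12) label the repeated-measures ANOVA as within group, and the footnote to Table 8 does the same for the paired t-test. The between-arm tests in those tables, in Table 9 and in the protocol's Statistical Analysis section are unadjusted two-sample or chi-square tests.

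**The concern.** A paired t-test, Wilcoxon signed-rank test or Friedman test asks whether patients changed from their own baseline. In a placebo-controlled trial that mixes any drug effect with time trend, background therapy and regression to the mean. Finding significance in one arm and not in the other is not evidence that the arms differ.

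Repeated-measures ANOVA could carry a group-by-time term, but none is stated and the tables show it was run within arms. The iron-profile line is ambiguous, because Kruskal-Wallis compares independent groups yet is listed for a pre/post comparison. Read alone, section 6 therefore yields no explicit drug-versus-placebo result for six of the eight primary endpoints.

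The two that do get a between-arm test have no baseline adjustment. For calcification the arms already differed before treatment, so the 12-month comparison carries that gap forward and could be read as a drug effect. The stratification factors enter no model.

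**Working it through.** **Calcification: reproducing the printed figures.** Tables 5 and 9, control n=41, study n=38.

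| | Control | Study | Gap (points) | Chi-square p, uncorrected | Printed p | Mann-Whitney p on grade |
|---|---|---|---|---|---|---|
| Baseline | 3 (7.3%) | 11 (28.9%) | 21.6 | 0.0119 | 0.012 | 0.014 |
| 12 months | 1 (2.4%) | 11 (28.9%) | 26.5 | 0.0010 | 0.001 | 0.0016 |

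Grades (none, minimal, mild, moderate) are [38,1,1,1] vs [27,3,7,1] at baseline and [40,0,0,1] vs [27,9,2,0] at 12 months. The share of the 12-month gap present before treatment is 21.6/26.5 = 82%.

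**What the planned test does with no drug effect, given this baseline.** Suppose that in both arms a share d of calcified patients resolve and a share g of the others become calcified. The expected 12-month gap is then 21.6 × (1 − d − g): 21.6 points at d=g=0, and 21.6 × 0.45 = 9.7 points at d=0.5, g=0.05. The documents give no transition rates, so d and g are assumptions. The unadjusted Mann-Whitney test, simulated from the tabulated baseline grades (10,000 trials per setting), rejects in:

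- 100% of trials with no change;
- 53% if half of calcified patients drop one grade and 5% of the others gain one;
- about 22% if half resolve fully and 5% of the others gain one.

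Over ten such settings (6,000 trials each), rank ANCOVA on baseline grade rejects in at most 3.5% and an exact test stratified by baseline calcification in at most 2.5%. These rates are conditional on the observed imbalance. Over re-randomisation (100,000 permutations of the pooled 12-month grades) the Mann-Whitney test rejects in 5.7%, near nominal.

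**What adjustment would give.** Let s of the 11 study patients calcified at 12 months (s=0 to 11), and c of the 1 control patient (c=0 or 1), also have been calcified at baseline. That makes 24 possible tables. The Mantel-Haenszel weights are 11×3/14 = 2.357 (calcified at baseline) and 27×38/65 = 15.785 (not calcified), sum 18.142.

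- Smallest (s=11, c=1): (11/11 − 1/3) × 2.357 / 18.142 = 0.087.
- Largest (s=0, c=0): (11/27 − 1/38) × 15.785 / 18.142 = 0.332.

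The stratified risk difference thus lies between 8.7 and 33.2 points, against 26.5 unadjusted. The Cochran-Mantel-Haenszel p-value is 0.0001 to 0.021 uncorrected, up to 0.040 exact, and up to 0.078 with continuity correction (7 of 24 tables above 0.05). All of this rests on 3 calcified control patients at baseline and 1 at 12 months.

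**Hepcidin.** Table 8: control 198±74 to 128±63, study 182±76 to 116±15. The changes are −70 and −66, each with p=0.001, and the between-arm p at 12 months is 0.2. The difference in change is +4 ug/L. With Var(change) = s0² + s1² − 2r·s0·s1 in each arm, r=0.5 gives 4783 and 4861, so SE = √(4783/41 + 4861/38) = 15.6 and the 95% CI is −27 to +35. The correlation r is assumed; r=0 gives −35 to +43 and r=0.8 gives −21 to +29.

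**Other within-arm results.** In Table 6, creatinine has p=0.01 (study) and 0.1 (control) within arms, but 0.8 between arms at 12 months. eGFR falls significantly in both arms: 100.3 − 114 = −13.7 in control and 115.7 − 128 = −12.3 in study, a difference in change of +1.4. That is illustrative only, because a t-test on the printed means and SDs gives between-arm p=0.26 at baseline and 0.14 at 12 months where 0.6 and 0.9 are printed. In a simulation with the same true change in both arms (normal data, assumed correlation 0.5, 41 vs 38), the two paired tests disagree on significance in 36% of trials at a 0.2 SD change and 49% at 0.3 SD.

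**Body weight (secondary).** Table 1: 78.9±14 vs 90±15 kg. The gap is 11.1 kg with SE = 14.49 × √(1/41 + 1/38) = 3.26, so t=3.40, p=0.001, 95% CI 4.6 to 17.6. The printed p is 0.5.

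**The case against.** Between-arm testing is not absent from the documents. The protocol plans unpaired t, Mann-Whitney and chi-square tests, and Tables 6 to 9 print a 12-month between-arm p-value for all eight primary endpoints. That is true and limits the point to section 6 and to adjustment. But those tests are also unadjusted, and section 6 does not assign them to the renal or haematological endpoints or to hepcidin.

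Randomisation makes an unadjusted test valid on average, and the 5.7% above confirms it. That stands as a statement about the procedure. It does not help in reading this trial, where the gap in a primary endpoint is known.

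The 22% to 100% range depends on assumed transitions, and 22% is not a floor: with 80% full resolution and 5% gain the rate is about 8%. That setting fits poorly, since it implies 14×0.2 + 65×0.05 = 6 calcified patients at 12 months against 12 printed. The range remains illustrative.

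No printed conclusion is shown to change. This also stands: the uncorrected and exact stratified p-values stay below 0.05 in every possible table, and approximate ANCOVA from the summaries is non-significant for eGFR (p 0.24 to 0.34) and hepcidin (0.36 to 0.52) at assumed correlations of 0.3 to 0.9. Nor do within-arm tests mislead everywhere; the printed within-arm haemoglobin and erythropoietin p-values all exceed 0.05.

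Finally, the secondary objective is exploratory, so within-patient tests partly fit it, and urine protein could be read as covered by the renal heading and the Friedman clause. Friedman still cannot compare arms.

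**Conclusion.** The concern holds and must be fixed. Section 6, followed as written, states no between-arm contrast for six of eight primary endpoints and a baseline-adjusted one for none. This is a wrong choice of stated tests, not merely missing detail, because the trial was sized for a difference between arms.

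For calcification, 21.6 of 26.5 points pre-date treatment, and the adjusted difference (8.7 to 33.2 points) cannot be recovered from the tables. The demonstrated problem is a misstated effect size and conditional error rate, not a proven false signal of harm. The counts and p-values for calcification rest only on printed data. The conditional rejection rates rest on assumed transitions, and the hepcidin interval on an assumed correlation.

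**What to change.** Amend section 6 so that the analysis of each SAP efficacy endpoint is a between-arm, baseline-adjusted contrast with a 95% CI, with one method fixed per endpoint before refitting:

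- Creatinine, eGFR, 24-hour urine protein, haemoglobin, weight and BMI: mixed model with treatment, visit, treatment-by-visit, baseline value, age and gender, reporting the 12-month difference (log scale for creatinine and urine protein).
- Hepcidin, erythropoietin, BNP, ferritin, TSAT and echocardiography: ANCOVA with the same covariates, naming in advance which are log-transformed. This assumes baseline and 12-month values only, as tabulated; the protocol lists echocardiography under monthly evaluation, so confirm the schedule.
- Coronary calcification: rank ANCOVA (or a penalised or exact analysis; name one) adjusted for baseline grade only, because just 12 of 79 patients, one of them in control, are calcified at 12 months. Report the baseline-stratified risk difference with its CI as the effect estimate.

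Present within-arm changes as descriptive. Check the printed eGFR and body-weight summaries and p-values against patient data first. The protocol's composite primary endpoint is a separate matter.

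The cost is a SAP amendment and re-analysis; no new data are needed. The SAP (dated 11/3/2024) post-dates the study, which ran to November 2023, and already contains 12-month results. The revision must therefore be dated, labelled post hoc and reported beside the originally listed tests; it cannot be called prespecified.

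### SAP 6 plans independent-samples tests for before/after iron markers, and Table 8 names a different test that would suit ferritin poorly if it was run on raw values

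*SAP*

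**What the plan says.** SAP section 4 makes the iron profile a secondary endpoint: "Iron Profile: Serum ferritin and TSAT". Section 6 gives its analysis in one sentence: "Iron Profile: Analyzed pre- and post-intervention using ANOVA or Kruskal-Wallis for non-normally distributed variables".

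Other lines of section 6 are more specific. Body weight has "Body Weight and BMI: Compared over time using ANOVA for repeated measures". Hemoglobin and erythropoietin have "Paired t-test for hemoglobin and erythropoietin levels if data is normally distributed; otherwise, Wilcoxon signed-rank test". Creatinine and eGFR have repeated-measures ANOVA with Friedman as the fallback. The BNP and coronary calcification line names Mann-Whitney and says that the comparison is between groups.

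Table 8 in the SAP appendix prints ferritin and TSAT as median (min, max) at baseline and 12 months. One footnote covers the whole table. For the within-group p-values it says "Within group analysis (paired t test"); for the between-arm p-values, "Between group analysis (Student T test or Mann-Whitney) for continuous data, and chi-square test for categorical data".

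**The concern.** A patient's ferritin before and after treatment are two correlated values. Kruskal-Wallis and one-way ANOVA assume independent samples. Used for a before/after contrast with positive correlation, they have a true error rate below the nominal 5% and give up the precision that pairing offers. The iron line is the only before/after line in section 6 whose named tests are neither paired nor repeated-measures.

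The appendix then names a test that the section 6 sentence does not mention. A paired t-test on raw values works with mean differences, which for a variable as skewed as ferritin are dominated by the largest values. So the plan and the table disagree, and each route can miss a change in ferritin. Neither within-arm route estimates the randomised treatment effect.

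**Working it through.** **The plan's own figures.** Table 8 prints within-group p-values for ferritin of 0.5 (control) and 0.8 (study). They cannot be reproduced: there are no patient pairs, within-patient differences or correlation. What follows is an illustration under stated assumptions.

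**Inputs from Table 8.**

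| Ferritin | Median (min, max) | Max / median | ln(max/min) | Log SD |
|---|---|---|---|---|
| Control, baseline | 60 (13, 1113) | 18.6 | 4.45 | 1.02 |
| Control, 12 months | 75 (6, 2127) | 28.4 | 5.87 | 1.35 |
| Study, baseline | 33.5 (3, 1460) | 43.6 | 6.19 | 1.44 |
| Study, 12 months | 64 (3, 1311) | 20.5 | 6.08 | 1.42 |

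Log SD is ln(max/min) divided by the expected range of n standard normal values (about 4.28 for n=38, 4.34 for n=41). Table 8 prints no n; 41 and 38 come from the other appendix tables. For TSAT the maximum is only 2.2 to 4.1 times the median and the log SD about 0.5 to 0.6.

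**Assumptions not in the documents.** Lognormal values, a pre/post correlation ρ on the log scale, and two-sided 0.05 (the SAP states this for primary analyses only). The true ratio is set to the ratio of study-arm medians, 64/33.5 = 1.91, so the log shift is 0.647.

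**Why ignoring pairing changes the error rate.** On the log scale the mean difference has variance 2σ²(1−ρ)/n, but an independent-samples test uses 2σ²/n. Its true size is therefore about 2Φ(−1.96/√(1−ρ)):
- ρ = 0.3: 1.96/0.837 = 2.34, size about 1.9%.
- ρ = 0.6: 1.96/0.632 = 3.10, size about 0.2%.

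**Simulation, n=38, log SD 1.4** (accurate to a point or two for power).

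| | ρ = 0 | ρ = 0.3 | ρ = 0.6 |
|---|---|---|---|
| Kruskal-Wallis, type I error | 5% | 2% | 0.3% |
| Kruskal-Wallis, power | 49% | 51% | 50% |
| Paired t on raw values, power | 27% | 32% | 44% |
| Signed-rank on log differences, power | 48% | 64% | 87% |
| Paired t on logs, power | 50% | 66% | 88% |

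Check of the last row at ρ = 0.6: the SD of the log difference is 1.4 × √0.8 = 1.252; 0.647 × √38 / 1.252 = 3.19; the critical t value on 37 df is 2.03; power is about Φ(1.16) = 88%. Signed-rank on raw differences is weaker than on log differences (42% at ρ = 0, 55% at 0.3) but still well above the raw paired t-test.

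**TSAT.** With the control-arm ratio 28/23.8 = 1.18, log SD 0.5, n=41 and ρ = 0.5, power is 46% for the raw paired t-test, 49% for signed-rank and 53% for the paired t-test on logs, so skewness costs little. Ignoring the pairing still matters: Kruskal-Wallis has 24%.

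**Between-arm illustration for ferritin.** The ratio of fold-changes is (64/33.5)/(75/60) = 1.91/1.25 = 1.53, log 0.424, taking medians as stand-ins for geometric means. The variance of a within-patient log change is s₀² + s₁² − 2ρs₀s₁.
- ρ = 0.6: study 1.636, control 1.211; SE = √(1.636/38 + 1.211/41) = 0.269; 95% CI 0.9 to 2.6.
- ρ = 0.3: study 2.863, control 2.037; SE = √(2.863/38 + 2.037/41) = 0.354; 95% CI 0.76 to 3.1.

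Both intervals include 1. A higher correlation would narrow them: at ρ = 0.8 the SE is √(0.818/38 + 0.660/41) = 0.194 and the interval 1.04 to 2.24. With ρ unknown, the illustration settles nothing.

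**The case against.** **The sentence may mean a comparison of arms at each time point.** Kruskal-Wallis on two arms is then valid and equivalent to Mann-Whitney, and Table 8 does print such p-values (ferritin 0.09 at baseline, 0.4 at 12 months; TSAT 0.05 and 0.1). This reading is possible but strained: the sentence speaks of before and after, and the BNP line says so when groups are compared. Even then, the 12-month comparison ignores each patient's baseline, although the baseline medians differ (ferritin 60 v 33.5, TSAT 23.8 v 18). What stands is that the fault is partly ambiguity.

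**The test run on ferritin is not established.** One footnote covers five variables, and footnotes here are not always literal: Table 6 labels every within-group p-value as repeated-measures ANOVA, including a categorical row. This stands. The sponsor should say which test was used; the printed p-values are not shown to be wrong.

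**A reader might infer that a real rise in ferritin was hidden**, since the study-arm median nearly doubles while p is 0.8. The documents do not support that. A shift in group medians is not a within-patient change. Under the model above, with a true ratio of 1.91, the raw paired t-test gives p of 0.75 or more in about 4% of data sets at ρ = 0.6 (7% at 0.3), against about 20% with no change. If p=0.8 came from that test, it leans towards no change. Nor is it right that the test cannot detect such a change, since its power is low but not nil, or that two or three patients decide the result, which the tables cannot show.

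**The benefit depends on an unknown correlation.** This stands: at ρ = 0 pairing gains nothing. The weakness of the raw paired t-test for ferritin remains at every correlation tried.

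**Conclusion.** The concern holds in a limited form. As worded, the iron sentence pairs a before/after question with tests for independent samples and specifies no between-arm contrast. The Table 8 footnote names yet another test. Under the before/after reading, the error rate is wrong whenever the two values are positively correlated: about 2% at correlation 0.3 and 0.3% at 0.6, instead of 5%. If a paired t-test was run on raw ferritin, it has about half the power of the same test on logs (27 v 50%, 32 v 66%, 44 v 88%). The skewness argument applies to ferritin and hardly to TSAT.

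These sizes rest on a lognormal shape, log SDs inferred from printed ranges, and a correlation that the documents do not give. No missed effect or changed conclusion is shown. Severity is low to moderate: the endpoint is secondary, under an objective worded as exploratory, and unadjusted between-arm p-values are already printed.

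**What to change.** Replace the iron sentence in SAP section 6. Compare 12-month log ferritin and log TSAT between arms in a model with the patient's own log baseline, and report the ratio of geometric means with a 95% CI. The printed minima (3 for ferritin, 5 for TSAT) are positive, so logs are defined. If a rank check is wanted, use Mann-Whitney on within-patient log change. Delete Kruskal-Wallis. Treat any within-arm test (signed-rank or paired t-test on logs) as descriptive only.

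State which tests produced the ferritin and TSAT p-values in Table 8, reconcile the footnote with section 6, and re-run the within-arm ferritin test if a raw-scale paired t-test was used.

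The cost is one sentence, one footnote and a re-run of two variables on data already collected. The downside is timing. The SAP is dated 11/3/2024, gives the study period as ending in November 2023, and already contains results. The revised iron analysis must therefore be labelled post hoc and shown beside the existing figures.
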